12.2.5 Expected and Unexpected Adverse Events

“Expected” AEs are those that have been previously reported as associated with the disease process. In addition, adverse events associated documented potential risk identified in Section 13.0 of this protocol will be noted as “Expected”. All others are to be recorded as “Unexpected”.

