12.2 Recording Adverse Events

Adverse events that occur during Study Medication administration will be recorded. Terms should be recorded consistently, using acceptable medical terms. When possible, a diagnosis should be identified as the AE (i.e., disease or syndrome) rather than the component signs and symptoms, and recorded on the case report form (e.g., record congestive heart failure rather than dyspnea, rales and cyanosis). However, signs and symptoms considered unrelated to encountered syndromes or diseases are to be recorded as individual AEs (e.g., if congestive heart failure and severe headaches are observed at the same time, each experience is to be recorded as an individual AE). The AE should not be recorded as a procedure or clinical measurement (i.e., a laboratory or vital sign) but should reflect the reason for the procedure or diagnosis.

Death is considered to be an outcome of an AE. The cause of death (rather than the term “death”) should be recorded on the serious AE and death report case report forms.

Subjects should be encouraged to report AEs spontaneously or in response to general, non-directed questioning. At each required visit (or whenever reported) during the study, all AEs that have occurred since the previous visit must be recorded on the AE case report form.

All AEs, regardless of seriousness, severity, or presumed relationship to the treatment must be recorded using medical terminology.

All AEs must be followed until resolution or until a stable clinical endpoint is reached. All measures required for AE management and the ultimate outcome of the AE must be recorded in the study document. All adverse events that occur in the study population will be tabulated and summarized.

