12.2.3 Relationship to Study Medication

The Principal Investigator is required to assess whether there is a reasonable possibility that the Study Medication caused or contributed to an AE.

Many terms and scales are used to describe the degree of causality between a Study Medication and an event. The expression “reasonable causal relationship” is meant to convey in general that there are facts (evidence) or arguments to suggest a causal relationship (ICH E2A, III/A/1).

Determination of whether there is a reasonable possibility that a treatment caused or contributed to an AE includes assessing temporal relationships, biologic plausibility, association (or lack of association) with underlying disease, and presence (or absence) of a more likely cause.

As is recommended in FDA draft guidance document, Safety Reporting Requirements for INDs and BA/BE Studies (2010), we define four degrees of relatedness: “unrelated”, “probably not related”, “suspected adverse drug reaction” (SADR) or “adverse reaction”.

Unrelated (clearly not related to the research)

The occurrence of the AE is not reasonably related in time, OR the AE is considered unlikely to be related to the treatment (biologically implausible).

Probably not related (doubtfully related to the research)

The administration of the treatment and the AE are not considered reasonably related in time AND the AE could also be explained by causes other than the treatment (concurrent illness/underlying disease, other drugs or procedures).

Suspected Adverse Drug Reaction (SADR)

Suspected adverse reaction means any AE for which there is a reasonable possibility that the treatment caused the AE. A ‘reasonable possibility’ means there is evidence to suggest a causal relationship between the treatment and the AE. A SADR reaction implies a lesser degree of certainty about causality than adverse reaction, which means any AE caused by a treatment.

The Principal Investigator should consider if exposure to the treatment and the AE are reasonably related in time AND the treatment is more likely than other causes to be responsible for the AE or is the most likely cause of the AE.

Adverse Reaction

An adverse reaction means any adverse event caused by a drug. Adverse reactions are a subset of all suspected adverse reactions for which there is reason to conclude that the treatment caused the event.

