12.3 Reporting of Adverse Events

12.3.1 Function of the Medical Monitor and FDA

An Independent Medical Monitor will be selected to oversee study safety. A detailed medical Monitoring plan will be submitted to FDA upon appointment of this individual and before the first subject is treated. This individual is to be an appropriately certified physician experienced in monitoring clinical trials.

The Principal Investigator will be responsible for confirming the severity of all adverse events. All serious events will be reported to the Independent Medical Monitor within 24 hours of their disclosure to the Principal Investigator. The Medical Monitor will review data or events reported by the Study Team within 72 hours of disclosure to the Medical Monitor.

During this time, appropriate care will be given to the study subject. If managing adverse events requires unblinding to the any member of the Study Team, the appropriate team member will disclose the group identity to the necessary medical provider.

The IRB will be notified of unanticipated and serious adverse events within 5 business days of identification. This reporting may come from the Study Team, the Independent Medical Monitor, or both.

Investigator Sponsor will notify FDA in an IND safety report (Form 3500A), unexpected fatal or life threatening suspected adverse reactions where there is evidence to suggest a causal relationship between the Study Medication and the adverse event will be reported as a serious suspected adverse reaction. This will be reported to the FDA no later than 7 calendar days after the sponsor-investigator's initial receipt of the information about the event.

Other unexpected serious suspected adverse reactions, where there is evidence to suggest a causal relationship between the Study Medication and the adverse event, will be reported as a serious suspected adverse reaction. This will be reported to the FDA on FDA Form 3500A no later than 15 calendar days after the sponsor-investigator's initial receipt of the information.

The sponsor must identify all IND safety reports previously submitted to FDA concerning a similar suspected adverse reaction and must analyze the significance of the suspected adverse reaction in light of previous, similar reports or any other relevant information.

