13.1 Associated with Fisetin Administration

Based upon the review of the published literature, pre-clinical data and available clinical data, we do not anticipate the occurrence of serious adverse events related to the prescribed regimen of Fisetin (FIS) in this study. However, potential side effects include the following:

- Reduced appetite,
- Altered activity,
- Nausea,
- Dry mouth,
- Diarrhea,
- Vomiting,
- Fatigue.
- There have been positive findings with Fisetin in the Ames and micronucleus assays.

In addition, FIS has been demonstrated to have inhibitory activity of cytochrome P450, and to have adverse interaction with caffeine, tobacco/nicotine consumption for which we have established exclusion criteria. These are listed in detail in **Section 9.1.2** of this protocol. In addition, a list of possible drug interactions with FIS are provided in **Section 22.4, Appendix D** of this document.

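### Section 12.2.5 calls an event Expected by its type alone, so, read literally, a serious suspected fisetin reaction recorded only as a Section 13.1 symptom would get no 7- or 15-day FDA report

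*Combined protocol and SAP*

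**What the plan says.** All references are to the combined protocol and SAP.

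- **Section 12.2.5** has two ways for an event to be Expected. One is a previously reported association with the disease. The other covers the listed risks: "adverse events associated documented potential risk identified in Section 13.0 of this protocol will be noted as" Expected. Every other event is Unexpected.
- **Section 13.1** gives eight bullets. Seven are symptoms: reduced appetite, altered activity, nausea, dry mouth, diarrhea, vomiting and fatigue. The eighth is a laboratory assay finding (Ames and micronucleus). The lead-in says "we do not anticipate the occurrence of serious adverse events related to the prescribed regimen of Fisetin (FIS) in this study".
- **Section 12.3.1** sets two FDA clocks. The 7-day report is for "unexpected fatal or life threatening suspected adverse reactions where there is evidence to suggest a causal relationship". The 15-day report is for "Other unexpected serious suspected adverse reactions, where there is evidence to suggest a causal relationship between the Study Medication and the adverse event". Separately, all serious events go to the Medical Monitor within 24 hours, and "The IRB will be notified of unanticipated and serious adverse events within 5 business days of identification".
- **Section 12.2** gives a recording rule: "When possible, a diagnosis should be identified as the AE (i.e., disease or syndrome) rather than the component signs and symptoms".

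**The concern.** Expectedness decides whether FDA hears of a serious suspected reaction in days or in a later progress report. For that purpose the label should separate the mild form of a listed symptom from a form that puts someone in hospital. Section 12.2.5 does not do this, although the five-grade severity scale stands immediately before it in 12.2.4.

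The result sits badly with Section 13.1. The protocol says it anticipates no serious fisetin reactions. The label would nevertheless treat the first one as Expected if it were recorded under a listed symptom. Safety is the primary endpoint of this Phase 1-2 trial, and prior human exposure in Section 5.4 is 36 subjects. A first serious suspected reaction would therefore be informative, and prompt reporting of it matters.

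**Working it through.** No arithmetic beyond simple counts applies, and the plan gives no figure to reproduce. The check traces one event through the definitions.

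**Example.** A subject is hospitalized for vomiting after dosing. No diagnosis beyond vomiting is established, and the investigator suspects the Study Medication.

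1. *Is it serious?* Yes. Hospitalization is one of the outcomes in 12.2.6.
2. *Is it a suspected reaction?* Yes. In 12.2.3 ("we define four degrees of relatedness") the investigator places it in one of the two upper categories, suspected adverse drug reaction or adverse reaction.
3. *Is it Expected?* Under 12.2.5, yes. Vomiting is a Section 13.1 risk and the rule has no further condition. Of the seven symptoms in 13.1, 0 carry a severity limit.
4. *Does the 15-day report apply?* Not on the literal text, because the trigger requires the event to be unexpected.
5. *If it were life-threatening or fatal?* The 7-day trigger has the same requirement and fails in the same way.
6. *Does another stated FDA route with a deadline apply?* None appears in 12.3.1. FDA would see the event through the progress reports in 16.4.6.

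**How far the gap reaches.**

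- If a diagnosis is recorded, as 12.2 prefers, the term is usually no longer a 13.1 symptom. The event is then Unexpected unless the diagnosis is itself tied to osteoarthritis or another Section 13.0 risk.
- An unlisted finding, such as the creatinine rise described in 5.4, is already Unexpected.
- The Medical Monitor's 24-hour notice covers all serious events whatever their label, and "The Medical Monitor will review data or events reported by the Study Team within 72 hours of disclosure to the Medical Monitor". Section 14.2 lets the Monitor stop enrollment with no expectedness condition.
- The IRB notice depends on whether the event was anticipated. Section 13.1 says serious fisetin events are not, so the notice probably applies. Section 16.2 also requires prompt reporting of unanticipated problems involving risk.

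**Size.** The documents give no rate for such a reaction. Section 5.4 reports 0 serious events in 32 + 4 = 36 treated subjects. The number affected is probably 0 or 1. That is a judgment, not an estimate from a model.

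**The case against.** The strongest reply is that the literal reading is not the natural one. Section 13.1 first says that serious fisetin events are not anticipated and only then lists side effects. Section 12.2.3 describes Section 13.0 as discussing events common with the medication. On that view the list documents only ordinary forms, so a hospitalized case is not a documented risk and is already Unexpected. This is a reasonable reading, but 12.2.5 does not state it. Table 13.11 scores the potential impact of fisetin administration at 3 (severe). That is a single score for the whole category and does not document serious vomiting, but it keeps the text from settling the matter.

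A second reply is that 12.2.5 governs how events are recorded, and that 12.3.1 does not refer back to it. That is true, but the protocol offers no other definition of unexpected, so staff would apply this one.

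A third reply is that 16.0 and 16.1 bind the investigator to applicable regulations, and that monitoring under 17.0 checks compliance with federal requirements. This stands as a real safeguard. The documents do not reproduce what those rules say about expectedness, so its effect cannot be checked here. It does not remove the ambiguity in the working text.

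A reader might also infer something stronger: that serious fisetin reactions could escape safety oversight, or that the stopping rules are disabled. The documents do not support either. The Monitor's notice, review and stopping power do not depend on the label. Section 14.1 is discretionary. A non-life-threatening listed symptom would fall outside 14.1(1) on the literal reading, and a life-threatening one might not, depending on whether unexpected qualifies both adjectives.

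**Conclusion.** The point holds as a minor wording defect. Applied literally, 12.2.5 together with 12.3.1 withholds the expedited FDA report for a serious suspected fisetin reaction whose only recorded term is a Section 13.1 symptom. This conflicts with the statement in 13.1 that no such events are anticipated.

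The conclusion rests on two assumptions: that unexpected in 12.3.1 carries the 12.2.5 meaning, and that no diagnosis replaces the symptom. The medical monitoring plan is not among the documents and could already deal with the matter.

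The consequence is delay in one channel, for probably 0 or 1 event. It is not a loss of safety oversight, and the documents give no basis for attaching a probability to it.

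**What to change.** Add one sentence to 12.2.5: *A suspected adverse reaction to Study Medication is Unexpected if its nature, severity or seriousness goes beyond what Section 13.1 describes; no serious reaction to Fisetin is currently expected.*

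Use this definition in 12.3.1 and wherever else expectedness appears, including the treatment-group comparison in 15.5.1, so that the trial has a single definition.

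Leave 14.1(1) as it is. Making every serious event that cannot be ruled unrelated Unexpected would go too far. It could draw in hospitalizations that come from the disease, such as the joint replacements foreseen in 15.5.2.4. The sentence above avoids this because it applies only to suspected reactions. No new case report form field is needed.

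The cost is one sentence and possibly one additional expedited report. Because 14.1(1) uses the same word, such an event could also come under that discretionary criterion. If the investigator invoked it, 14.0 would halt enrollment and dosing until the IRB allowed a restart, so a false alarm would not be free.

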12.2.6 Serious Adverse Events

An AE or suspected adverse reaction is considered “serious” if, in the view of either the Principal Investigator, it results in any of the following outcomes:

- Death;
- A life-threatening adverse event;
- Hospitalization;
- Disability or permanent damage;
- Congenital anomaly/birth defect;
- Other serious events that may jeopardize the patient and may require medical or surgical intervention (treatment) to prevent one of the other outcomes.

An AE or suspected adverse reaction is considered “life-threatening” if, (in the view of the Principal Investigator) its occurrence places the patient or subject at immediate risk of death. It does not include an AE or suspected adverse reaction that, had it occurred in a more severe form, might have caused death.

Serious and/or unexpected adverse event(s) may present as either a local or systemic response, or both, which may present as an anaphylactic response associated with generalized urticaria, shortness of breath, or respiratory or circulatory arrest.

Subjects will be instructed to contact the study site immediately if a systemic reaction occurs between scheduled study visits. Subjects may be assessed initially over the phone and may be asked to return to the study site for an additional visit to assess the reaction.

12.3 Reporting of Adverse Events

12.3.1 Function of the Medical Monitor and FDA

An Independent Medical Monitor will be selected to oversee study safety. A detailed medical Monitoring plan will be submitted to FDA upon appointment of this individual and before the first subject is treated. This individual is to be an appropriately certified physician experienced in monitoring clinical trials.

The Principal Investigator will be responsible for confirming the severity of all adverse events. All serious events will be reported to the Independent Medical Monitor within 24 hours of their disclosure to the Principal Investigator. The Medical Monitor will review data or events reported by the Study Team within 72 hours of disclosure to the Medical Monitor.

During this time, appropriate care will be given to the study subject. If managing adverse events requires unblinding to the any member of the Study Team, the appropriate team member will disclose the group identity to the necessary medical provider.

The IRB will be notified of unanticipated and serious adverse events within 5 business days of identification. This reporting may come from the Study Team, the Independent Medical Monitor, or both.

Investigator Sponsor will notify FDA in an IND safety report (Form 3500A), unexpected fatal or life threatening suspected adverse reactions where there is evidence to suggest a causal relationship between the Study Medication and the adverse event will be reported as a serious suspected adverse reaction. This will be reported to the FDA no later than 7 calendar days after the sponsor-investigator's initial receipt of the information about the event.

Other unexpected serious suspected adverse reactions, where there is evidence to suggest a causal relationship between the Study Medication and the adverse event, will be reported as a serious suspected adverse reaction. This will be reported to the FDA on FDA Form 3500A no later than 15 calendar days after the sponsor-investigator's initial receipt of the information.

The sponsor must identify all IND safety reports previously submitted to FDA concerning a similar suspected adverse reaction and must analyze the significance of the suspected adverse reaction in light of previous, similar reports or any other relevant information.

13.0 Potential Risks to Study Subjects and Risk Mitigation

Expected risks to subjects in this study include all those currently associated with osteoarthritis (OA) of the knee and its progression. Additional risk to subjects which might arise as the result of study participation are discussed below.

13.1 Associated with Fisetin Administration

Based upon the review of the published literature, pre-clinical data and available clinical data, we do not anticipate the occurrence of serious adverse events related to the prescribed regimen of Fisetin (FIS) in this study. However, potential side effects include the following:

- Reduced appetite,
- Altered activity,
- Nausea,
- Dry mouth,
- Diarrhea,
- Vomiting,
- Fatigue.
- There have been positive findings with Fisetin in the Ames and micronucleus assays.

In addition, FIS has been demonstrated to have inhibitory activity of cytochrome P450, and to have adverse interaction with caffeine, tobacco/nicotine consumption for which we have established exclusion criteria. These are listed in detail in **Section 9.1.2** of this protocol. In addition, a list of possible drug interactions with FIS are provided in **Section 22.4, Appendix D** of this document.

13.2 Risk Associated with Placebo Administration

If results of this study reveal that administration of FIS improves OA symptoms and/or joint structure, subjects randomized to placebo may miss these benefit(s).

All subjects will be fully informed that they have only a 50% chance of being randomized to receive FIS. In addition, subjects will be told that the advantages of receiving FIS in the treatment of OA in humans are unknown.

13.3 Associated with MRI

The MRI scan involves exposure to loud noise and positioning in a small space. Subjects may feel claustrophobic, fatigued or nauseated especially if they are uncomfortable with tight spaces. The MRI scan does not involve the use of x-rays or injectable dyes. There are no known reports of increased cancer or birth defects associated with this procedure. The MRI scan exposes the subject to high magnetic fields, which can be dangerous for those with pacemakers and some metal implants.

All subjects will be carefully screened for potential contraindications for MRI. Subjects will be provided with hearing protection and may listen to their choice of streamed music for comfort. MRI-compatible padding and/or blankets may be used as requested for subject comfort. Subjects will be provided with a 'squeeze ball' activated microphone to allow communication with the MRI technologists so that they can notify the technologist of any problems or the desire or need to abort the scan.

13.4 Associated with PRO Questionnaires

The completion of numerous PRO questionnaires can be laborious and uncomfortable presenting a potential risk of emotional distress.

Whenever possible PRO questionnaires will be completed remotely through electronic link in order to minimize time needed to complete questionnaires. The subject will be told that he/she may discontinue questionnaire completion at any time if the questionnaire causes emotional distress.

13.5 Associated with Physical Exam

There is a potential risk of pain and/or discomfort. Palpation and low-magnitude manual force applied to the knee could result in mild to moderate discomfort, depending upon a subject's subjective perception of discomfort and knee condition.

Care will be taken to limit this discomfort to not exceed that experienced during normal daily activities such as walking, climbing stairs, putting on shoes, etc. Only experienced, trained clinicians will perform the exam, and the exam will be modified if the subject indicates

more than mild discomfort. The exam will be stopped if the subject indicates moderate or greater discomfort or requests that the exam be stopped.

13.6 Associated with Blood Draw

The potential risks of blood draw include fatigue, light-headedness, nausea, vasovagal syncope, pain at the insertion site, damage to the blood vessels, erythema, and or potential infection.

To avoid such occurrences, blood draws will be performed only by persons qualified by license and experience.

